11.3. Data Analyses Plans

11.3.1. Analysis of the Conduct of the Trial

Enrollment, major protocol deviations, and discontinuations for the trial will be summarized using a CONSORT diagram.

11.3.2. Patient Disposition

A detailed description of patient disposition will include:

- A summary of data on patient discontinuation from treatment.
- A summary of data on overall qualification status of all patients.
- An account of all identified protocol deviations.

All patients enrolled in the study will be included in the summation. An evaluable patient is any patient who has received any number of doses of both agents (vemurafenib + sorafenib) and has a scan after at least 2 cycles of treatment. The number of patients who do not qualify for analysis, who die or discontinue before treatment begins, will be specified.

11.3.3. Analysis of Patient Characteristics

Patient characteristics will include a summary of the following:

- Patient demographics
- Baseline disease characteristics
- Pre-existing conditions
- Prior therapies
- Concomitant medications and treatments
- Other patient characteristics will be summarized as appropriate.

11.3.4. Statistical Analysis

The primary efficacy analysis will focus on the disease control rate (CR + PR + SD at 16 weeks). Secondary endpoints include progression-free survival (PFS) and overall survival (OS). The efficacy analysis will only be conducted on patients who have received any number of doses of both agents (vemurafenib + sorafenib) and have a scan after at least 2 cycles of treatment.

Objective responses will be evaluated using the Response Evaluation Criteria In Solid Tumors 1.1 (RECIST 1.1). Changes (i.e. improvements) in tumor measurements from baseline values will be assigned a status of CR or PR or SD. Objective response measurements will comprise the sum of CR plus PR. The overall response rate, as well as the rates for the individual categories of response (i.e. CR, PR, SD, and PD), will be estimated by the percentage of patients achieving these criteria with exact 95% binomial confidence intervals.

Progression-free survival is defined as the interval from the date of study treatment initiation (C1/D1) to the earliest date of documented evidence of recurrent or progressive disease, or the date of death due to any cause, whichever occurs first. Overall survival will be measured from the date of study treatment initiation (C1/D1) to the date of death

due to any cause, or the date of last contact (censored observations). For the estimation of progression-free and overall survival a Kaplan-Meier analysis will be performed.

Longitudinal measurements of circulating tumor DNA (ctDNA) and phospho ERK will be visualized using plots for each evaluable patient. These measurements will be transformed using a logarithmic transformation, if necessary, to remove skewness. Significant changes across time will be assessed using linear mixed effects models, to account for the correlation among the measurements within an individual. If the observed change is non-linear, nonlinear mixed effects models will be used.

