7.3. Progression Free Survival (PFS)

Progression-free survival (PFS) is defined as the time from study treatment initiation (C1/D1) to first documentation of objective tumor progression or to death due to any

cause. In the absence of previous documentation of objective tumor progression will be censored at the last date the patient was known to be progression-free in those who do not have objective tumor progression and who are: 1) still on study at the time of an analysis; 2) are given anti-tumor treatment other than the study treatment; or 3) are removed from study follow-up prior to documentation of objective tumor progression.

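### PFS and OS are timed from C1/D1 but analysed only in patients scanned after 2 cycles, which guarantees about 8 weeks of OS and raises the PFS curve

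*Combined protocol and SAP*

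**What the plan says.** Section 11.3.4 makes disease control the primary endpoint and PFS and OS secondary endpoints. The next sentence sets the analysis population for all of them: "The efficacy analysis will only be conducted on patients who have received any number of doses of both agents", "and have a scan after at least 2 cycles of treatment".

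The same section fixes the time origin: "Overall survival will be measured from the date of study treatment initiation (C1/D1) to the date of death". Section 7.3 does the same for PFS: "Progression-free survival (PFS) is defined as the time from study treatment initiation (C1/D1) to first documentation of objective tumor progression", or to death from any cause. The estimator is stated without qualification: "For the estimation of progression-free and overall survival a Kaplan-Meier analysis will be performed".

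Other sections bear on this as follows:
- **Timing.** A cycle is 28 days (5.1), and the first scheduled tumour assessment is before cycle 3 (6.3.3).
- **Replacement.** Patients without the qualifying scan are replaced (5.9). Up to 24 may be enrolled to obtain at most 12 evaluable (11.2).
- **Populations.** Sections 7.3 and 7.4 name no other population for PFS or OS. The only all-treated set is for safety (7.2, 11.3.5).
- **Corrections.** No landmark, delayed-entry or all-treated analysis of PFS or OS is planned.

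**The concern.** A patient joins the PFS and OS analysis because of something that happens at about week 8, yet follow-up is counted from week 0. Anyone who dies in between is left out, and those who remain are credited with weeks in which they could not have died and still been counted. This is guarantee-time (immortal-time) bias, and plain Kaplan-Meier does not correct it.

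Section 3.2 uses PFS and OS to describe the regimen's clinical activity. Followed as written, the plan gives an OS curve that is too high at every time after week 8, for as long as any patient dies before then. The PFS curve is raised because early deaths and most early progressors are dropped.

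**Working it through.** **Plan's own figures.** The documents state no PFS or OS figure to reproduce. The two-stage design in 11.2 does reproduce (type I error 0.0188, power 0.9077), but it does not bear on this point.

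**Guaranteed time.** 2 cycles × 28 days = 56 days = 8 weeks, apart from visit windows (72 hours in 6.3).

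**OS.** Let S(t) be true survival from C1/D1. If the only effect of the restriction is to remove deaths before week 8, the reported curve is 1 up to week 8 and S(t)/S(8) afterwards. Every later probability is therefore multiplied by 1/S(8). For a Weibull curve with shape k and true median m, the reported median is m × [1 + (8/m)^k]^(1/k). With k = 1 (constant hazard) this is m + 8.

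The medians below are assumptions.

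| True OS median (weeks) | S(8), k = 1 | 1/S(8) | Reported median, k = 1 | S(26), true → reported, k = 1 | Reported median, k = 1.5 |
|---|---|---|---|---|---|
| 12 | 0.630 | 1.59 | 20 | 0.223 → 0.354 | 16.0 |
| 16 | 0.707 | 1.41 | 24 | 0.324 → 0.459 | 19.6 |
| 20 | 0.758 | 1.32 | 28 | 0.406 → 0.536 | 23.2 |

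For m = 16 and k = 1: S(8) = 2^(−8/16) = 0.707 and S(26) = 2^(−26/16) = 0.324, so 0.324/0.707 gives the reported 0.459 (unrounded inputs). For m = 16 and k = 1.5: (8/16)^1.5 = 0.354, and 16 × 1.354^(2/3) = 19.6.

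The rise is 8 weeks under a constant hazard and 4.0, 3.6 and 3.2 weeks with k = 1.5. A falling hazard (k = 0.8) gives more: 12 becomes 23.7 and 16 becomes 28.2.

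**PFS.** Progression is found mainly at scans, so the OS formula does not carry over. It was simulated instead (400,000 patients per row). Latent progression and death were independent and exponential, progression was detected at the next 8-weekly scan, deaths were counted when they occurred, and patients alive past week 8 were treated as evaluable.

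| Latent progression / OS median (weeks) | Event-free just after week 8, all → evaluable | Median PFS, all → evaluable | 24-week restricted mean, all → evaluable |
|---|---|---|---|
| 6 / 14 | 0.265 → 0.394 | 8.0 → 8.0 | 8.84 → 11.31 |
| 8 / 16 | 0.352 → 0.499 | 8.0 → 8.0 | 9.99 → 12.58 |
| 8 / 20 | 0.377 → 0.498 | 8.0 → 8.0 | 10.63 → 12.81 |
| 12 / 26 | 0.508 → 0.629 | 8.7 → 16.0 | 12.75 → 14.86 |

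The restricted mean rises by 2.1 to 2.6 weeks. The median stays at 8.0 in three of the four rows, because the drop at the first scheduled scan sets it. In the fourth row the curve is still above one half after that scan, and the median jumps to the next one. The simulation removes early deaths only, not early progressors who leave without the qualifying scan.

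**The case against.** The strongest case on the other side concerns scope and importance, and much of it stands.

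- **PFS median.** A reader might infer that median PFS also rises by 8 weeks. The documents do not support this. Scheduled scans first show progression at about week 8 in any population, and patients who progress at that scan are evaluable. Someone with progression on an earlier unscheduled scan (6.3.3) could also be continued at discretion (6.6), be scanned again and enter with PFS below 8 weeks.
- **Share of early events.** A reader might infer that a large share of deaths falls before week 8, or that half the patients will be lost this way. No early event rate is given, and entry requires ECOG 0 or 1 with adequate organ function. The allowance of 24 enrolled for 12 evaluable is an upper bound on exclusions, and toxicity or withdrawal also exclude patients.
- **Historical comparison.** A reader might infer that the results will be set against published series. No such comparison is planned.
- **Data in hand.** This is true for survival (5.7, 6.5, Appendix A footnote 12) but not fully for progression. The off-treatment visit has no scan, and follow-up after it records survival, not progression.
- **Visibility.** Early deaths are not hidden. Disposition covers all enrolled patients (11.3.1, 11.3.2) and deaths are listed in the safety set (11.3.5). This helps the reader but does not correct the curves.
- **Precision.** With 12 deaths and an estimated exponential median of 16 weeks, the 95% interval is about 10 to 31 weeks (16 × 24 divided by the chi-square quantiles on 24 degrees of freedom). The bias lies within that range, but imprecision does not excuse a known upward bias.

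None of this removes the OS defect.

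**Conclusion.** The point holds for OS and, in a weaker form, for PFS.

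OS carries about 8 weeks of guaranteed survival, apart from visit windows. Counting only the removal of deaths before week 8, every later OS probability is inflated by 1/S(8). Under assumed true medians of 12 to 20 weeks, the reported median rises by 8 weeks if the hazard is constant and by about 3 to 4 weeks with Weibull shape 1.5. The direction follows from the text; the size depends on medians and hazard shapes that the documents do not give. Exclusions for other reasons are not in these figures.

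For PFS the curve is raised, but a shift in the median is not established.

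This is a should-fix. PFS and OS are secondary, no test is planned on them, and neither the two-stage rule nor the stopping criteria in 11.4 use them.

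**What to change.** In 11.3.4:

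1. Estimate OS and PFS by Kaplan-Meier from C1/D1 in all treated patients. State whether this means at least one dose of both agents, matching the dosing condition in 11.3.4, or of either agent, as in the 11.3.5 safety set. The two can differ.
2. Leave the PFS event definition alone. It already counts death from any cause, so early deaths become events once the population is widened.
3. Keep evaluable-only curves as supplementary, started at a week-8 landmark or with delayed entry at the scan date. For PFS, say how a progression found on the qualifying scan itself is counted, because it falls at the entry time.
4. Report the number of patients who stopped before week 8 without post-baseline imaging, with reasons.

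**Cost.** For OS this is wording only, since survival follow-up already covers these patients, and the reported estimates will be lower. For PFS the change recovers early deaths and any progression seen on an unscheduled scan. It does not recover progression that was never imaged. Under 7.3 those patients will be censored early, possibly informatively, which is why item 4 is needed.

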After the adjustment based upon the NTF from May 13, 2022, we will examine 5 more patients at a reduced dose. If at least one patient of the five demonstrated a partial response (overall response rate of $\geq 20\%$), we will proceed with enrolling 7 more patients. Simon's two-stage design (Simon, 1989) will be used. The null hypothesis that the true response rate is 0% will be tested against a one-sided alternative. In the first stage, n=5 patients will be accrued. If there are zero patients with a response (either a PR or CR) in these 5 patients, the study will be stopped. Otherwise, 7 additional patients will be accrued for a total of 12. The null hypothesis will be rejected if 3 or more patients have a response (either PR or CR) in 12 patients.

Table of Contents

1. BACKGROUND AND RATIONALE.....	21
1.1. Disease Background and Introduction	21
1.2. Rationale of Clinical Trial	22
1.3. Study Agent(s) Background and Associated Known Toxicities	22
1.3.1. Vemurafenib	22
1.3.2. Sorafenib	23
1.4. Clinical Experience with Reported Phase I Trial with Vemurafenib + Sorafenib 23	
2. HYPOTHESIS	24
3. STUDY OBJECTIVES	24
3.1. Primary Objectives	24
3.2. Secondary Objectives	24
3.3. Exploratory Objectives	25
3.4. Endpoints	25
3.4.1. Primary Endpoint	25
3.4.2. Secondary Endpoint	25
3.4.3. Exploratory Endpoint	25
4. STUDY POPULATION	25
4.1. Inclusion Criteria	25
4.2. Exclusion Criteria	26
5. STUDY TREATMENT	28
5.1. Treatment Dosage and Administration	28
5.2. Administration of Vemurafenib + Sorafenib	28
5.3. Toxicities and Dosing Delays / Dose Modifications	29
5.3.1. Vemurafenib Dose Modifications	29
5.3.2. Sorafenib Dose Modifications	Error! Bookmark not defined.
5.4. Concomitant Medications / Treatments	32
5.5. Concomitant Therapies Requiring Caution	33
5.5.1. Vemurafenib	33
5.5.2. Sorafenib	33
5.6. Duration of Therapy	34
5.7. Duration of Follow-up	34

5.8.	Removal of Subjects from Protocol Therapy	34
5.9.	Subject Replacement	34
6.	STUDY PROCEDURES	35
6.1.	Screening / Baseline Procedures	35
6.2.	Optional Tissue Collection	36
6.3.	Procedures During Treatment (Cycle is 28 Days)	36
6.3.1.	Day 1 of Each Cycle	36
6.3.2.	Day 3 (Cycle 1 Only)	Error! Bookmark not defined.
6.3.3.	Days 8, 15 and 22 of Each Cycle	37
6.3.4.	Tumor Assessments Every 2 Cycles (Every 8 Weeks)	37
6.4.	Off Treatment Visit – to be Completed 14-28 (+/-2) Days From the Last Dose of Study Treatment	37
6.5.	Follow-up Procedures	38
6.6.	Study Treatment Discontinuation	38
7.	MEASUREMENT OF EFFECT	39

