11.2. Sample Size and Accrual

Between 7 and 12 evaluable patients total will be entered into this study. To obtain that number of evaluable patients we estimate up to 24 patients will possibly be enrolled. An evaluable patient is defined as one that receives at least one dose of both agents (vemurafenib + sorafenib) and has a scan after at least 2 cycles of treatment. We are hoping for a disease control rate of $\geq 40\%$. Simon's two-stage design (Simon, 1989) will be used. The null hypothesis that the true response rate is 5% will be tested against a one-sided alternative. In the first stage, $n=7$ patients will be accrued. If there are zero responses in these 7 patients, the study will be stopped. Otherwise, 5 additional patients will be accrued for a total of 12. The null hypothesis will be rejected if 3 or more responses are observed in 12 patients. This design yields a type I error rate of 0.0188 and power of 0.9077 when the true response rate is 40%. (Jung et al, 2004).

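### Section 11.3.4 gives fixed-sample percentages and exact intervals for a two-stage trial and names no estimator or interval for the primary DCR; adding a two-stage interval, p-value and supplementary estimate is a cheap improvement

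*Combined protocol and SAP*

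**What the plan says.** Section 11.2 states that "Simon's two-stage design (Simon, 1989) will be used" and that "The null hypothesis that the true response rate is 5% will be tested against a one-sided alternative". The stage 1 rule is "If there are zero responses in these 7 patients, the study will be stopped", followed by "Otherwise, 5 additional patients will be accrued for a total of 12". The null is rejected at 3 or more of 12, with stated type I error 0.0188 and power 0.9077 at 40%. Section 11.4 ties the stop to disease control at 16 weeks in the first 7 evaluable patients.

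The Statistical Methods part of the trial synopsis sets a different rule, on PR or CR: "In the first stage, n=5 patients will be accrued". It stops at zero responses and otherwise adds 7 patients to reach 12, against a null of 0%.

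Section 11.3.4 makes DCR the focus of the primary analysis. Its estimation sentence, however, covers only the overall response rate (ORR) and the separate CR, PR, SD and PD rates, as percentages "with exact 95% binomial confidence intervals". The documents give no estimate, interval or p-value that allows for two-stage sampling.

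**The concern.** There are two gaps.

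- **The primary endpoint has no stated estimator or interval.** DCR cannot be assembled from the listed categories, because the SD category in that sentence carries no stated 16-week condition.
- **The methods that are stated treat the sample size as fixed.** When a trial stops only on zero events, low results are frozen at zero with a small denominator and cannot recover in stage 2. The raw proportion then averages below the truth. An interval computed as if 7 or 12 had been fixed in advance also does not follow the order of the possible outcomes.

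What is at stake is the reported rate and its interval, mainly when the final count is 1 or 2 of 12.

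**Working it through.** **Inputs.** From 11.2: n1 = 7, n2 = 5, stop at 0, reject at 3 or more of 12, null 5%, target 40%. From the synopsis: n1 = 5, n2 = 7, stop at 0, reject at 3 or more of 12. X1 and X2 are the event counts in the two stages and p is the true rate.

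**Step 1. Reproduce the plan's figures.** P(X1 ≥ 1 and X1 + X2 ≥ 3) under 7+5 is 0.01876 at p = 0.05 and 0.90767 at p = 0.40. Both match 11.2. A single-stage rule of 3 of 12 gives 0.0196 and 0.9166. So the design figures use the two-stage outcome space, and the estimation sentence does not.

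**Step 2. Bias of the raw proportion for the endpoint that drives the stop.** A stop has probability (1−p)^n1 and contributes zero events, so

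E[raw] = p − (n2/12)·p·(1−p)^n1.

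The bias is largest at p = 1/(n1+1), which is 12.5% for 7+5 and 16.7% for 5+7.

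| True rate | Bias, 7+5 | Bias, 5+7 |
|---|---|---|
| 5% | −1.5 points | −2.3 points |
| 20% | −1.7 points | −3.8 points |
| 40% | −0.5 points | −1.8 points |
| Maximum | −2.05 points (at 12.5%) | −3.9 points (at 16.7%) |

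**Step 3. The rates that 11.3.4 does name, if the 7+5 stop is on DCR.** With ORR = r and DCR = q, the bias in ORR is −(5/12)·r·(1−q)^7. The documents give no expected ORR, so these rates are assumptions:

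- r = 5%, q = 20%: −0.4 points
- r = 10%, q = 20%: −0.9 points
- r = 10%, q = 40%: −0.1 points

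The PD rate moves the other way: +1.7 points at q = 20%, if every patient without disease control counts as PD.

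**Step 4. Upper 95% limits.**

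- 0 of n1: 1 − 0.025^(1/n1), which is 41.0% for 0/7 and 52.2% for 0/5.
- 1/12, ordinary: solve (1−p)^12 + 12p(1−p)^11 = 0.025, giving 38.5%.
- 1/12, two-stage: solve (1−p)^n1 + n1·p(1−p)^11 = 0.025, giving 43.2% (7+5) or 52.5% (5+7).

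The ordinary limit falls when the result improves from a futility stop to 1/12. The two-stage limit rises.

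**Step 5. UMVUE and intervals.** For a final count s reached in stage 2,

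UMVUE = Σ C(n1−1, x−1)·C(n2, s−x) / Σ C(n1, x)·C(n2, s−x), summed over x ≥ 1.

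For 7+5 this is 1/7 at s = 1, 11/56 at s = 2 and 55/210 at s = 3.

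| Result | Raw | UMVUE 7+5 | UMVUE 5+7 | Ordinary 95% | Two-stage 7+5 | Two-stage 5+7 |
|---|---|---|---|---|---|---|
| 1/12 | 8.3% | 14.3% | 20.0% | 0.2–38.5% | 0.4–43.2% | 0.5–52.5% |
| 2/12 | 16.7% | 19.6% | 24.4% | 2.1–48.4% | 2.3–49.5% | 2.5–54.5% |
| 3/12 | 25.0% | 26.2% | 29.7% | 5.5–57.2% | 5.6–57.4% | 5.8–59.3% |

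One-sided p-values against 5% under 7+5, two-stage and fixed-sample: 0.103 and 0.118 at 2/12; 0.0188 and 0.0196 at 3/12.

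**Step 6. Coverage of the ordinary interval.** On a fine grid of p the 7+5 minimum is 94.8%. Coverage is below 95% only for p of about 41.0% to 42.8%. The 5+7 minimum is 95.3%.

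**Step 7. Behaviour of the UMVUE.** Given that stage 2 opens, its mean is p / (1 − (1−p)^n1), and the raw mean is E[raw] / (1 − (1−p)^n1).

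- 7+5, p = 5%: UMVUE 16.6%, raw 11.8%
- 7+5, p = 20%: UMVUE 25.3%, raw 23.1%
- 5+7, p = 20%: UMVUE 29.8% (0.2/0.67232 = 0.2975), raw 24.1%

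The root mean squared error over all 7+5 outcomes is 7.9 points for the UMVUE and 6.3 for the raw rate at p = 5%, and 10.4 and 9.6 at p = 10%. From p = 20% upward the UMVUE does better.

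**The case against.** The case for leaving 11.3.4 alone has five parts.

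- **Relevance.** Under 7+5 the estimation sentence concerns ORR and the response categories, while the stop is on DCR. The bias in ORR is then under 1 point at the assumed rates, and PD is biased upward. This stands: it is wrong to read every rate in that sentence as biased downward by 2 points. Under the synopsis rule, PR or CR drives the stop, and the full 5+7 bias applies to ORR.
- **Convention.** Raw proportions with exact binomial limits are a defensible description of 12 patients, and the formal decision rule already uses the two-stage design. This stands too, and it is why the raw proportion should stay.
- **Size.** At 3/12 the estimate moves 1.2 points (7+5) inside an interval about 52 points wide, and both lower limits exceed 5%. A reader might infer that the bias is worst where the go/no-go decision falls. The figures do not support that. The bias peaks at a true rate of 12.5% (7+5) or 16.7% (5+7), and the UMVUE departs most from the raw rate at 1/12 and 2/12, below the cutoff.
- **Coverage.** A reader might infer that the planned intervals are invalid. They are not: they are mostly conservative, with a worst shortfall of 0.2 points.
- **Remedy.** Replacing the raw rate with the UMVUE is a trade-off. At 1/12 under 7+5 it equals 1/7 and gives no weight to the five stage 2 failures. Step 7 shows it does worse once stage 2 opens. This stands, so the UMVUE belongs in a supplementary role.

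None of this answers the missing estimator for DCR or the out-of-order upper limits.

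**Conclusion.** The point holds as a minor improvement. Section 11.3.4 needs an estimator and interval for DCR in any case, and the fixed-sample intervals do not match the two-stage design.

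The downward bias for the endpoint that drives the stop is at most 2.05 points (7+5) or 3.9 points (5+7). It is an average over all outcomes, early stops included; given that stage 2 opens, the raw rate averages above the truth. The clearest defect is the reversed upper limits: 41.0% then 38.5% under 7+5, and 52.2% then 38.5% under 5+7. The decision at 3/12 is unchanged under either rule.

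These figures assume that the stage 1 rule is followed exactly as written, that outcomes are independent with a common rate, and that there is no discretionary stop of the kind 11.4 also permits. The size depends on which rule governs, and the synopsis and sections 11.2 and 11.4 leave that unreconciled.

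**What to change.** First reconcile the synopsis with 11.2 and 11.4, so that one design, one endpoint and one null drive the stop. The null matters here: against the synopsis value of 0%, a single response gives a p-value of zero, so a p-value is informative only against a non-zero null.

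Then amend 11.3.4, for DCR and for whichever endpoint drives the stopping rule, to:

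- keep the raw proportion;
- add a two-stage exact 95% interval and one-sided p-value computed for the design actually run (7+5 or 5+7), with stage 1 stops ordered lowest;
- report the UMVUE as a supplementary estimate beside the raw rate, not in its place.

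The ordinary intervals can remain for the descriptive response categories.

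The cost is a sentence or two of analysis-plan text and a few lines of code. The downside is a second estimate to explain, one that overestimates more than the raw rate when stage 2 opens and has larger error at low true rates.
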